10.3.4. Reporting of SAEs

SAE Reporting to Pfizer Safety via an Electronic Data Collection Tool

- The primary mechanism for reporting an SAE to Pfizer Safety will be the electronic data collection tool.
- If the electronic system is unavailable, then the site will use the paper SAE data collection tool (see next section) to report the event within 24 hours.
- The site will enter the SAE data into the electronic system as soon as the data become available.
- After the study is completed at a given site, the electronic data collection tool will be taken off-line to prevent the entry of new data or changes to existing data.
- If a site receives a report of a new SAE from a study participant or receives updated data on a previously reported SAE after the electronic data collection tool has been taken off-line, then the site can report this information on a paper SAE form (see next section) or to Pfizer Safety by telephone.

SAE Reporting to Pfizer Safety via CT SAE Report Form

- Facsimile transmission of the CT SAE Report Form is the preferred method to transmit this information to Pfizer Safety.
- In circumstances when the facsimile is not working, notification by telephone is acceptable with a copy of the CT SAE Report Form sent by overnight mail or courier service.
- Initial notification via telephone does not replace the need for the investigator to complete and sign the CT SAE Report Form pages within the designated reporting time frames.

10.4. Appendix 4: Contraceptive and Barrier Guidance

10.4.1. Male Participant Reproductive Inclusion Criteria

Male participants are eligible to participate if they agree to the following requirements during the intervention period and for at least 28 days after the last dose of study intervention, which corresponds to the time needed to eliminate reproductive safety risk of the study intervention(s):

- Refrain from donating sperm.

PLUS either:

- Be abstinent from heterosexual intercourse with a female of childbearing potential as their preferred and usual lifestyle (abstinent on a long-term and persistent basis) and agree to remain abstinent.

OR

- Must agree to use contraception/barrier as detailed below:
 - Agree to use a male condom when having sexual intercourse with a woman of childbearing potential who is not currently pregnant.
 - In addition to male condom use, a highly effective method of contraception may be considered in WOCBP partners of male participants (refer to the list of highly effective methods below in [Section 10.4.4](#)).

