5. STUDY POPULATION

This study can fulfill its objectives only if appropriate participants are enrolled. The following eligibility criteria are designed to select participants for whom participation in the study is considered appropriate. All relevant medical and nonmedical conditions should be taken into consideration when deciding whether a particular participant is suitable for this protocol.

Prospective approval of protocol deviations to recruitment and enrollment criteria, also known as protocol waivers or exemptions, is not permitted.

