5.1. Inclusion Criteria

Participants are eligible to be included in the study only if all of the following criteria apply:

Age and Sex:

1. Female participants of non-childbearing potential and/or male participants must be 18 to 55 years of age, inclusive, at the time of signing the ICD.
 - Refer to [Appendix 4](#) for reproductive criteria for male ([Section 10.4.1](#)) and female ([Section 10.4.2](#)) participants.

Type of Participant and Disease Characteristics:

2. Male and female participants who are overtly healthy as determined by medical evaluation including a detailed medical history, complete physical examination, vital signs which include BP and pulse rate measurement, clinical laboratory tests, and ECG.
3. Participants who are willing and able to comply with all scheduled visits, treatment plan, laboratory tests, lifestyle considerations, and other study procedures.

Weight:

4. BMI of 17.5 to 30.5 kg/m²; and a total body weight >50 kg (110 lb).

Informed Consent:

5. Capable of giving signed informed consent as described in [Appendix 1](#), which includes compliance with the requirements and restrictions listed in the ICD and in this protocol.

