5.2. Exclusion Criteria

Participants are excluded from the study if any of the following criteria apply:

Medical Conditions:

1. Evidence or history of clinically significant hematological, renal, endocrine, pulmonary, gastrointestinal (eg, ulcerative colitis, irritable bowel syndrome, Crohn's disease), cardiovascular, hepatic, psychiatric, neurological, dermatological, or allergic disease (including drug allergies, but excluding untreated, asymptomatic, seasonal allergies at the time of dosing).
2. Any condition possibly affecting drug absorption (eg, gastrectomy, cholecystectomy).
3. History of HIV infection, hepatitis B, or hepatitis C; positive testing for HIV, HBsAg, HBcAb or HCVAb. As an exception, a positive HBsAb as a result of participant vaccination is permissible.
4. Other medical or psychiatric condition including recent (within the past year) or active suicidal ideation/behavior or laboratory abnormality that may increase the risk of study participation or, in the investigator's judgment, make the participant inappropriate for the study.
5. A history of hypersensitivity to the active compounds or to any inactive ingredients (excipients) contained in the formulations.

Prior/Concomitant Therapy:

6. Use of prescription or nonprescription drugs and dietary and herbal supplements within 7 days or 5 half-lives (whichever is longer) prior to the first dose of study intervention.

Proton pump inhibitors must be discontinued at least 14 days prior to the first dose of study medication.

Hormone replacement therapy must be discontinued at least 28 days prior to the first dose of study intervention.

Refer to [Section 6.8](#) for additional details.

Prior/Concurrent Clinical Study Experience:

7. Previous administration with an investigational drug within 30 days (or as determined by the local requirement) or 5 half-lives preceding the first dose of study intervention used in this study (whichever is longer).

Diagnostic Assessments:

8. A positive urine drug test.
9. Screening supine BP ≥ 140 mm Hg (systolic) or ≥ 90 mm Hg (diastolic), following at least 5 minutes of supine rest. If BP is ≥ 140 mm Hg (systolic) or ≥ 90 mm Hg (diastolic), the BP should be repeated 2 more times and the average of the 3 BP values should be used to determine the participant's eligibility.

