10. Baseline 12-lead ECG that demonstrates clinically relevant abnormalities that may affect participant safety or interpretation of study results (eg, baseline QTcF interval >450 msec, complete LBBB, signs of an acute or indeterminate age- myocardial infarction, ST-T interval changes suggestive of myocardial ischemia, second or -third-degree AV block, or serious bradyarrhythmias or tachyarrhythmias). If the baseline uncorrected QT interval is >450 msec, this interval should be rate corrected using the Fridericia method and the resulting QTcF should be used for decision making and reporting. If QTcF exceeds 450 msec, or QRS exceeds 120 msec, the ECG should be repeated 2 more times and the average of the 3 QTcF or QRS values should be used to determine the participant's eligibility. Computer-interpreted ECGs should be overread by a physician experienced in reading ECGs before excluding participants.

11. Participants with **ANY** of the following abnormalities in clinical laboratory tests at screening, as assessed by the study-specific laboratory and confirmed by a single repeat test, if deemed necessary:

- eGFR (CKD-EPI) <90 mL/min/1.73 m²;
- AST **or** ALT level > ULN;
- Serum (total and direct) bilirubin level > ULN; participants with a history of Gilbert's syndrome may have direct bilirubin measured and would be eligible for this study provided the direct bilirubin level is ≤ ULN;
- Amylase and lipase level > ULN.

Other Exclusions:

12. History of alcohol abuse or binge drinking and/or any other licit or illicit drug use or dependence within 6 months of Screening. Binge drinking is defined as a pattern of 5 (male) and 4 (female) or more alcoholic drinks in about 2 hours. As a general rule, alcohol intake should not exceed 14 units per week (1 unit = 8 ounces [240 mL] beer, 1 ounce [30 mL] of 40% spirit or 3 ounces [90 mL] of wine).

13. Use of tobacco/nicotine containing products, electronic smoking device in excess of the equivalent of 5 cigarettes/day.

14. Male participants with partners currently pregnant; male participants able to father children who are unwilling or unable to use a highly effective method of contraception as outlined in this protocol for the duration of the study and for at least 28 days after the last dose of IP.

15. Blood donation (excluding plasma donations) of approximately 1 pint (500 mL) or more within 60 days prior to dosing.

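### Section 10.4.1 makes a highly effective contraceptive method optional for male participants, while Sections 2.3.1, 4.2, 5.2 (criterion 14) and 5.3.4 treat it as mandatory

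*Protocol*

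**What the plan says.** Protocol Section 5.1, criterion 1, refers to Appendix 4 "for reproductive criteria for male" participants, naming Section 10.4.1. That section opens: "Male participants are eligible to participate if they agree to the following requirements during the intervention period and for at least 28 days". The 28 days run from the final dose. Every man must refrain from donating sperm. Beyond that he must either be abstinent or meet the contraception bullets. The first of these is mandatory: "Agree to use a male condom when having sexual intercourse with a woman of childbearing potential who is not currently pregnant". The second is permissive: "In addition to male condom use, a highly effective method of contraception may be considered in WOCBP partners of male participants".

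Exclusion criterion 14 in Section 5.2 removes "male participants able to father children who are unwilling or unable to use a highly effective method of contraception as outlined in this protocol". It covers the whole study and at least 28 days beyond the final dose.

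Three other sections take the same line as exclusion 14:

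- Section 2.3.1 gives the exclusion of such men as part of the mitigation for risk to a fetus, and cites Sections 5.1, 5.2 and Appendix 4.
- Section 4.2 says men with partners of childbearing potential are required to use a highly effective method, and cites Appendix 4.
- Section 5.3.4 has the investigator or designee confirm that a method has been chosen from the Section 10.4.4 list, and tell the participant at scheduled visits that highly effective contraception is needed.

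**The concern.** The protocol answers one eligibility and conduct question in two ways. Section 4.2 states a requirement and cites an appendix that presents the same thing as optional. Section 2.3.1 relies partly on that appendix for its fetal-risk mitigation, and the appendix bullet is weaker than the mitigation described.

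Section 10.4.1 is the text a site will consult for the male criteria, because inclusion criterion 1 names it. A site working from it could tell a man that a condom is enough, and he could go through the study on that basis. What is at stake is exposure of a partner around the time of conception to a drug for which Section 2.3.1 reports reproductive toxicity in animals. No estimate or test in the trial depends on the point.

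**Working it through.** No arithmetic applies beyond counting the listed methods, so the check sets the texts side by side.

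**Step 1. Does a condom count as highly effective under this protocol?** Section 10.4.4 numbers five methods with low user dependency (1 to 5) and three that are user dependent (6 to 8), so 5 + 3 = 8. None is a condom. The condom appears only in the barrier list that follows, whose items are added to a user-dependent method. Section 10.4.1 draws the same line by placing a highly effective method on top of condom use. The answer is no.

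**Step 2. What does each section ask of a fertile, non-abstinent man whose partner is of childbearing potential and not pregnant?**

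| Protocol section | Condom | Highly effective method |
|---|---|---|
| 10.4.1 (via inclusion 1) | Required | Optional |
| 2.3.1 | Not mentioned | Excluded if he will not or cannot use one |
| 4.2 | Not mentioned | Required |
| 5.2, criterion 14 | Not mentioned | Excluded if he will not or cannot use one |
| 5.3.4 | Not mentioned | Method confirmed from the 10.4.4 list; man told of the need |

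Section 10.4.1 is the only one that makes the method optional. Abstinent men are not affected: 10.4.1 accepts abstinence, and it is method 8 in 10.4.4.

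**Step 3. How do the criteria combine?** Section 5.1: "Participants are eligible to be included in the study only if all of the following criteria apply". Section 5.2: "Participants are excluded from the study if any of the following criteria apply". Section 5: "Prospective approval of protocol deviations to recruitment and enrollment criteria, also known as protocol waivers or exemptions, is not permitted". Meeting 10.4.1 is therefore necessary for entry but not sufficient, and exclusion 14 applies as well.

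**Step 4. Apply this to two men who would rely on a condom.**

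- *He refuses, or is unable, to use any of the eight methods.* He meets 10.4.1 but exclusion 14 bars him. The combined rule is clear.
- *He is willing and able to use a listed method, but is told under 10.4.1 that it is optional and uses only a condom.* Exclusion 14 is worded around unwillingness or inability, so by its letter it does not clearly bar him. He meets 10.4.1. His conduct is contrary to 4.2 and 5.3.4.

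The second man is where the wording of 10.4.1 has a practical effect.

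**Step 5. What would catch him?** Section 5.3.4 requires confirmation of a listed method and a documented affirmation of its use. The Schedule of Activities reviews eligibility at Screening and on Day -1 of Period 1. It places contraception checks at Screening, Day -1, Day 4 or 5, Day 7, follow-up and early termination. A site that follows 5.3.4 would find the gap before the first dose.

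**The case against.** The strongest reply is that the operative rule is not in doubt. The criteria are cumulative, waivers are barred, and 10.4.1 is one necessary condition that nobody would read as overriding exclusion 14. For the man who refuses or cannot use a listed method, that is right. A reader might infer from 10.4.1 that the protocol opens a condom-only route of entry for men whom exclusion 14 bars. The documents do not support this.

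The reply does not cover the willing man in Step 4. The opposite inference, that exclusion 14 already bars every man who relies on a condom and so the bullet is harmless, goes beyond that criterion's wording.

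A second reply is that exclusion 14 and Section 2.3.1 refer to highly effective methods as set out in the protocol, and so defer to Appendix 4. They do, but the appendix leaves the condom off its list of eight and treats it as something separate. The deference does not make a condom sufficient.

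A third reply is that Section 5.3.4 and the repeated checks already protect partners. This stands, and it is why the practical risk is small. It does not remove the conflict, because site staff must choose between 5.3.4 and 10.4.1 when they advise a participant.

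Finally, 10.4.1 asks for a condom with every method, whereas 10.4.4 adds a barrier only to user-dependent ones. That difference is real and would remain after the fix. It concerns the condom, and a man who uses both a condom and a listed method satisfies both sections.

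**Conclusion.** The point holds as a minor internal inconsistency in a safety-related eligibility rule, and Section 10.4.1 is wrong as written. Four sections call for a highly effective method or exclude men who will not or cannot use one. The male criteria named by inclusion 1 make it optional.

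The practical consequence is confined to non-abstinent men able to father children, with partners of childbearing potential, who would use a listed method if told to but are told they need not. The documents do not say how many such men there might be, and no count can be derived. A reader might also infer that the fetal-risk mitigation as a whole fails. It does not: exclusion 14 and Section 5.3.4 are in force and the checks are scheduled. The PK estimates, the sample size of 28 and the planned analysis are untouched.

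The conclusion assumes that highly effective means the numbered list in 10.4.4, the only definition the protocol gives, and that exclusion 14 is read by its wording on unwillingness or inability.

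**What to change.** In Section 10.4.1, keep the condom bullet. Reword the bullet after it so that, in addition to the condom, a highly effective method *must be used with WOCBP partners of male participants able to father children (Section 10.4.4)*. Leave Sections 2.3.1, 4.2, 5.2 and 5.3.4 as they are, since they already agree with one another.

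The cost is one bullet in an appendix. Exclusion 14 already bars men who refuse or cannot use a listed method, so the change mainly affects what willing men are told to do. It adds no data collection and changes neither the sample size nor the SAP.

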10.4.2. Female Participant Reproductive Inclusion Criteria

A female participant is eligible to participate if she is not a WOCBP (see definitions below in Section 10.4.3).

The investigator is responsible for review of medical history, menstrual history, and recent sexual activity to decrease the risk for inclusion of a WOCBP.

10.4.3. Woman of Childbearing Potential

A woman is considered fertile following menarche and until becoming postmenopausal unless permanently sterile (see below).

If fertility is unclear (eg, amenorrhea in adolescents or athletes) and a menstrual cycle cannot be confirmed before the first dose of study intervention, additional evaluation should be considered.

Women in the following categories are not considered WOCBP:

1. Premenopausal female with 1 of the following:

- Documented hysterectomy;
- Documented bilateral salpingectomy;
- Documented bilateral oophorectomy.

For individuals with permanent infertility due to an alternate medical cause other than the above, (eg, mullerian agenesis, androgen insensitivity), investigator discretion should be applied to determining study entry.

Note: Documentation for any of the above categories can come from the site personnel's review of the participant's medical records, medical examination, or medical history interview. The method of documentation should be recorded in the participant's medical record for the study.

2. Postmenopausal female.

- A postmenopausal state is defined as no menses for 12 months without an alternative medical cause. In addition:
 - A high FSH level in the postmenopausal range must be used to confirm a postmenopausal state in women under 60 years old and not using hormonal contraception or HRT.
 - A female on HRT and whose menopausal status is in doubt will be required to use one of the nonestrogen hormonal highly effective contraception methods if they wish to continue their HRT during the study. Otherwise, they must discontinue HRT to allow confirmation of postmenopausal status before study enrollment.

10.4.4. Contraception Methods

Contraceptive use by men or WOCBP partners of male participants should be consistent with local availability/regulations regarding the use of contraceptive methods for those participating in clinical trials.

Highly Effective Methods That Have Low User Dependency

1. Implantable progestogen-only hormone contraception associated with inhibition of ovulation.
2. Intrauterine device.

3. Intrauterine hormone-releasing system.
4. Bilateral tubal occlusion (eg, bilateral tubal ligation).
5. Vasectomized partner.
 - A vasectomized partner is a highly effective contraceptive method provided that the partner is the sole sexual partner of the WOCBP and the absence of sperm has been confirmed. If not, an additional highly effective method of contraception should be used. The spermatogenesis cycle is approximately 90 days.

Highly Effective Methods That Are User Dependent

6. Combined (estrogen- and progestogen-containing) hormonal contraception associated with inhibition of ovulation.
 - Oral;
 - Intravaginal;
 - Transdermal.
7. Progestogen-only hormone contraception associated with inhibition of ovulation.
 - Oral;
 - Injectable.
8. Sexual abstinence.
 - Sexual abstinence is considered a highly effective method only if defined as refraining from heterosexual intercourse during the entire period of risk associated with the study intervention. The reliability of sexual abstinence needs to be evaluated in relation to the duration of the study and the preferred and usual lifestyle of the participant.

One of the following effective barrier methods must be used in addition to the highly effective methods listed above that are user dependent:

- Male or female condom with or without spermicide;
- Cervical cap, diaphragm, or sponge with spermicide;
- A combination of male condom with either cervical cap, diaphragm, or sponge with spermicide (double-barrier methods).

CCI

10.6. Appendix 6: Liver Safety: Suggested Actions and Follow-Up Assessments

Potential Cases of Drug-Induced Liver Injury

Humans exposed to a drug who show no sign of liver injury (as determined by elevations in transaminases) are termed “tolerators,” while those who show transient liver injury but adapt are termed “adaptors.” In some participants, transaminase elevations are a harbinger of a more serious potential outcome. These participants fail to adapt and therefore are “susceptible” to progressive and serious liver injury, commonly referred to as DILI. Participants who experience a transaminase elevation above $3 \times$ ULN should be monitored more frequently to determine if they are “adaptors” or are “susceptible.”

In the majority of DILI cases, elevations in AST and/or ALT precede TBili elevations ($>2 \times$ ULN) by several days or weeks. The increase in TBili typically occurs while AST/ALT is/are still elevated above $3 \times$ ULN (ie, AST/ALT and TBili values will be elevated within the same laboratory sample). In rare instances, by the time TBili elevations are detected, AST/ALT values might have decreased. This occurrence is still regarded as a potential DILI. Therefore, abnormal elevations in either AST OR ALT in addition to TBili that meet the criteria outlined below are considered potential DILI (assessed per Hy’s law criteria) cases and should always be considered important medical events, even before all other possible causes of liver injury have been excluded.

The threshold of laboratory abnormalities for a potential DILI case depends on the participant’s individual baseline values and underlying conditions. Participants who present with the following laboratory abnormalities should be evaluated further as potential DILI (Hy’s law) cases to definitively determine the etiology of the abnormal laboratory values:

- Participants with AST/ALT and TBili baseline values within the normal range who subsequently present with AST OR ALT values $>3 \times$ ULN AND a TBili value $>2 \times$ ULN with no evidence of hemolysis and an alkaline phosphatase value $<2 \times$ ULN or not available.
- For participants with baseline AST **OR** ALT **OR** TBili values above the ULN, the following threshold values are used in the definition mentioned above, as needed, depending on which values are above the ULN at baseline:
 - Preexisting AST or ALT baseline values above the normal range: AST or ALT values >2 times the baseline values AND $>3 \times$ ULN; or $>8 \times$ ULN (whichever is smaller).
 - Preexisting values of TBili above the normal range: TBili level increased from baseline value by an amount of at least $1 \times$ ULN **or** if the value reaches $>3 \times$ ULN (whichever is smaller).

Rises in AST/ALT and TBili separated by more than a few weeks should be assessed individually based on clinical judgment; any case where uncertainty remains as to whether it represents a potential Hy's law case should be reviewed with the sponsor.

The participant should return to the investigator site and be evaluated as soon as possible, preferably within 48 hours from awareness of the abnormal results. This evaluation should include laboratory tests, detailed history, and physical assessment.

In addition to repeating measurements of AST and ALT and TBili for suspected Hy's law cases, additional laboratory tests should include albumin, CK, direct and indirect bilirubin, GGT, PT/INR, total bile acids, and alkaline phosphatase. Consideration should also be given to drawing a separate tube of clotted blood and an anticoagulated tube of blood for further testing, as needed, for further contemporaneous analyses at the time of the recognized initial abnormalities to determine etiology. A detailed history, including relevant information, such as review of ethanol, acetaminophen/paracetamol (either by itself or as a coformulated product in prescription or over-the-counter medications), recreational drug, or supplement (herbal) use and consumption, family history, sexual history, travel history, history of contact with a jaundiced person, surgery, blood transfusion, history of liver or allergic disease, and potential occupational exposure to chemicals, should be collected. Further testing for acute hepatitis A, B, C, D, and E infection, liver imaging (eg, biliary tract), and collection of serum samples for acetaminophen/paracetamol drug and/or protein adduct levels may be warranted.

All cases demonstrated on repeat testing as meeting the laboratory criteria of AST/ALT and TBili elevation defined above should be considered potential DILI (Hy's law) cases if no other reason for the LFT abnormalities has yet been found. **Such potential DILI (Hy's law) cases are to be reported as SAEs, irrespective of availability of all the results of the investigations performed to determine etiology of the LFT abnormalities.**

A potential DILI (Hy's law) case becomes a confirmed case only after all results of reasonable investigations have been received and have excluded an alternative etiology.

